7.1.5.2 EQ-5D-5L for SRI, Randomization Phase and Treatment-naive Open-label Arm

The EQ-5D-5L (Appendix J) is a standardized instrument used to measure health outcome (EuroQol Group 1990) and consists of a 5-item questionnaire and a "thermometer" visual analog scale ranging from 0 (worst imaginable health state) to 100 (best imaginable health state). The scores for the 5 dimensions are used to compute a single utility score ranging from 0 to 1, representing the general health status of the individual. The 5 dimensions evaluated are mobility, self-care, usual activities, pain/discomfort, and anxiety/depression. The questionnaire will be administered on the same visit schedule as the FACT-Lym.

7.1.6 Medical Resource Utilization (MRU)

Medical resource utilization including hospitalizations, emergency department visits, and hematopoietic growth factor use will be collected for each treatment arm throughout the study treatment period.

7.2 Efficacy Evaluations

7.2.1 Overall Response Assessments

Overall response assessments will include physical examinations, recording of symptoms, hematological test results, bone marrow aspirate or bone marrow biopsy, CT/PET radiological evaluations and endoscopy per the schedule of assessments (Appendix A and Appendix B). Response assessments will be performed according to the Revised Criteria for Response Assessment of Malignant Lymphoma (Cheson 2014), as assessed by investigators (Appendix E) until disease progression or withdrawal of consent from the study.

7.2.2 Survival

After progression, survival status will be assessed approximately every 12 weeks until death, withdrawal by subject, or study terminated by Sponsor, whichever comes first. Data on the subsequent lines of anticancer therapy will be captured. Survival sweeps will be conducted at the time of the final analysis. All subjects who are on study and not known to have died prior to the survival sweep will be contacted at that time.

7.3 Sample Collection and Handling

The actual dates and times of sample collection must be recorded in source documents for transcription to the eCRF or laboratory requisition form. Refer to the Schedule of Assessments (Appendix A and Appendix B) for the timing and frequency of all sample collections.

Instructions for the collection, handling, and shipment of samples are found in the Laboratory Manual.

8 STUDY PROCEDURES

8.1 Screening Phase

Screening procedures will be performed up to 28 days before the first dose of ibrutinib and venetoclax/placebo, unless otherwise specified, and may be performed over more than 1 visit. All subjects must first read, understand, and sign the IRB/REB/IEC-approved ICF before any study-specific screening procedures are performed. After signing the ICF, Screening, and being deemed eligible for entry, subjects will be enrolled in the study.

8.1.1 Screening/Consenting Visit

The following procedures will be performed at the Screening Visit within 28 days prior to enrollment unless otherwise noted:

- Review of eligibility criteria
- Medical history including demographic information and prior treatments for MCL (if applicable)
- Collection of pathology report for cytogenetics/FISH documenting MCL diagnosis (if available)
- Collection of approximately 20 slides of fresh or most recent dated FFPE archival tumor biopsy tissue, OR tumor biopsy obtained by core needle biopsy prior to randomization
- Document bone marrow disease involvement (bone marrow biopsy must be obtained at Screening or up to 90 days before the first dose of study drug for disease confirmation)

- Record concomitant medications (including chemotherapy, radiation, over-the-counter drugs, vitamins, and herbs)
- Perform a complete physical examination, including height (may use prior height
 measurement if available in source documents), weight and examination of the skin,
 eyes, ears, nose, throat, lungs, heart, abdomen, extremities, musculoskeletal system,
 lymphatic system, and nervous system
- B-symptom assessment
- Obtain vital signs (including blood pressure, heart rate, and body temperature) after the subject has rested in the sitting position for ≥ 3 minutes.
- Evaluation of ECOG PS
- Determination of Medical Resource Utilization (MRU)
- Obtain a single 12-lead ECG after the subject has been in a supine position and resting for at least 10 minutes.
- AEs (record as Medical History on eCRF)
- Obtain bone marrow biopsy and aspirate (within 28 days prior to first dose) as described in Section 7.1.3.5
- Obtain blood specimens for the following laboratory tests
- Hematology
- o Blood chemistry (including creatinine clearance)
- Coagulation panel (PT/INR, aPTT)
- Hepatitis Serologies
- o Serum β2-microglobulin
- Urinalysis
- Obtain serum or urine pregnancy test for women of childbearing potential only
 - Imaging by CT and/or other modality as described in Section 7.1.3.2.
 - TLS risk assessment and prophylaxis within 72 hours of first dose of venetoclax
- o Serum creatinine, uric acid, potassium, phosphorus, calcium, and albumin, if available
- o Determination of level of risk and need for hospitalization
- Hydration: subject education
- o Prescription of allopurinol (and rasburicase for high risk subjects)

8.2 Treatment Phase

Following completion of the Screening Visit and once eligibility has been confirmed (per inclusion/exclusion criteria), subjects will initiate study treatment (see Section 5.2 for ibrutinib and venetoclax dosing).

Refer to the Schedule of Assessments (Appendix A and Appendix B) for a complete list of procedures to be performed at each scheduled study visit.

8.2.1 Treatment Visits for Standard Ramp-up Schedule for SRI, Randomization Phase, and Treatment-naive (TN) Open-label Arm

8.2.1.1 Week 1 Day 1 and Week 2 Day 1

Pre-dose (within 72 hours prior to the first venetoclax dose and before each dose increase)

- Confirmation of eligibility (per inclusion/exclusion criteria) at week 1 only.
- Update medical history at week 1 only
- AEs
- Concomitant medications (including chemotherapy, radiation, over-the-counter drugs, vitamins, and herbs)
- Physical examination
- Vital signs
- ECOG PS (Week 1 Day 1 only)
- PRO at week 1 only
- Determination of Medical Resource Utilization (MRU)
- TLS risk assessment and prophylaxis
- Hospitalization of subjects with high tumor burden
- Laboratory Tests
 - Hematology
 - Blood chemistry
 - Serum or urine pregnancy test (for women of childbearing potential only)
 (Week 1 Day 1 only)
 - o MRD peripheral blood (Week 1 Day 1 only)
 - o Biomarker blood sample (Week 1 Day 1 only)
 - o Buccal Swab (Week 1 Day 1 only)

Dosing – Week 1 Day 1 and Week 2 Day 1

The dose of venetoclax or placebo should not be administered until the blood chemistry results have been evaluated.

- In-clinic administration of venetoclax or placebo with a meal
- In-clinic administration of ibrutinib

Post-dose

- For hospitalized subjects, serum creatinine, uric acid, potassium, phosphorus, calcium, and albumin, if available should be monitored at 4±1, 8±1, 12±1 hours, after the venetoclax/placebo dose.
- For all outpatient subjects, serum creatinine, uric acid, potassium, phosphorus, calcium, and albumin, if available should be monitored at 6-8 hours after the venetoclax/placebo dose.
- Any changes in these parameters should be managed promptly and treatment modified before any further venetoclax/placebo is administered.

8.2.1.2 Week 1 Day 2 and Week 2 Day 2

Pre-dose

- AEs
- Concomitant medications (including chemotherapy, radiation, over-the-counter drugs, vitamins, and herbs)
- Vital signs
- Laboratory Tests
 - o Blood chemistry (creatinine, uric acid, potassium, phosphorus, calcium, and albumin, if available)
- TLS risk assessment and prophylaxis
- Determination of Medical Resource Utilization (MRU)

Dosing – Week 1 Day 2 and Week 2 Day 2

The dose of venetoclax/placebo should not be administered until the 24-hour blood chemistry monitoring results have been evaluated.

- In-clinic administration of venetoclax/placebo with a meal
- In-clinic administration of ibrutinib

8.2.1.3 Week 1 Day 3 and Week 2 Day 3 (Hospitalized Subjects Only)

Pre-dose

- AEs
- Concomitant medications (including chemotherapy, radiation, over-the-counter drugs, vitamins, and herbs)
- Laboratory Tests
 - o Blood chemistry monitoring (creatinine, uric acid, potassium, phosphorus, calcium, and albumin, if available)

- TLS risk assessment and prophylaxis
- Determination of Medical Resource Utilization (MRU)

Dosing – Week 1 Day 3 and Week 2 Day 3

The dose of venetoclax/placebo should not be administered until the blood chemistry monitoring results have been evaluated.

- In-clinic administration of venetoclax/placebo with a meal
- In-clinic administration of ibrutinib

Dosing - Week 1 Day 3 and Week 2 Day 3

The dose of venetoclax or placebo should not be administered until the blood chemistry monitoring results have been evaluated.

- In-clinic administration of venetoclax or placebo with a meal
- In-clinic administration of ibrutinib

8.2.1.4 Weeks 3, 4, and 5 Day 1 for Standard Ramp-up Schedule

Pre-dose

- AEs
- Concomitant medications (including chemotherapy, radiation, over-the-counter drugs, vitamins, and herbs)
- Physical examination
- Vital signs
- ECOG PS (Week 3 Day 1 only)
- Determination of Medical Resource Utilization (MRU)
- TLS risk assessment and prophylaxis
- Laboratory Tests
 - Hematology
 - o Blood chemistry
- Pharmacokinetics (only for TN open-label arm, on Week 4 Day 7). Pre-dose (\pm 30 min);

Dosing

The dose of venetoclax or placebo should not be administered until the blood chemistry results have been evaluated.

- In-clinic administration of venetoclax or placebo with a meal
- In-clinic administration of ibrutinib

Post-dose

- Blood chemistry monitoring (creatinine, uric acid, potassium, phosphorus, calcium, and albumin, if available)
- Post-dose 1 hour (±15 min), 2 hours (±15 min), 4 hours (±30 min), 6 hours (±30 min) and 8 hours (±1 hour) after the administration of ibrutinib and venetoclax
 - o For subjects with high tumor burden, serum creatinine, uric acid, potassium, phosphorus, calcium, and albumin, if available should be monitored at 6-8 hours after the start of the venetoclax or placebo dose at each ramp-up dose level. Any changes in these parameters should be managed promptly and treatment modified before any further venetoclax or placebo is administered.

8.2.1.5 Week 6 Day 1

Pre-dose

- AEs
- Concomitant medications (including chemotherapy, radiation, over-the-counter drugs, vitamins, and herbs)
- Physical examination
- Vital signs
- ECOG PS
- Determination of Medical Resource Utilization (MRU)
- TLS risk assessment and prophylaxis
- Laboratory Tests
 - Hematology
 - o Blood chemistry
 - o PK samples for ibrutinib and venetoclax or placebo

Dosing

- In-clinic administration of venetoclax or placebo with a meal
- In-clinic administration of ibrutinib

Post-dose

• PK samples for ibrutinib and venetoclax or placebo 1 hour (±15 min), 2 hours (±15 min), 4 hours (±30 min), 6 hours (±30 min) and 8 hours (±1 hour) after the administration of ibrutinib and venetoclax or placebo (see Section 7.1.4)

8.2.1.6 Week 8 Day 1 (\pm 1 Day) and Week 10 Day 1 (\pm 1 Day)

- AEs
- Concomitant medications (including chemotherapy, radiation, over-the-counter drugs, vitamins, and herbs)
- Physical examination
- Vital signs
- Determination of Medical Resource Utilization (MRU)
- TLS risk assessment and prophylaxis
- Laboratory Tests
 - Hematology
 - o Blood chemistry

Dosing

- In-clinic administration of venetoclax or placebo with a meal
- In-clinic administration of ibrutinib

8.2.1.7 Week 13 and beyond (± 7 Days)

- AEs
- Concomitant medications (including chemotherapy, radiation, over-the-counter drugs, vitamins, and herbs)
- PRO at response assessment visits (see Section 7.1.5 for all timepoints [Appendix I])
- Physical examination
- Vital signs
- ECOG PS
- Determination of Medical Resource Utilization (MRU)
- TLS risk assessment and prophylaxis
- Response Assessments

• For TN open-label arm only

- Week 13 mandatory PET scan for all subjects.
- o Week 25 mandatory PET scan for subjects in SD and PR at Week 13.
- o Week 49, mandatory PET scan for all subjects
- Laboratory Tests
 - Hematology
 - o Blood chemistry
- For TN open-label arm only
 - Week 13 Day 1: Pharmacokinetics. Pre-dose (±30 min); Post-dose 1 hour (±15 min), 2 hours (±15 min) after the administration of ibrutinib and venetoclax

After Week 13, clinic visits are scheduled every 4 weeks for one year; every 8 weeks during the second and third years; and every 12 weeks thereafter until treatment discontinuation. At each clinic visit subject should be supplied with enough study drug to last until the next clinic visit.

8.2.2 Response Evaluation

Response assessment visits should occur on Week 13 Day 1, then every 12 weeks for the first year; every 16 weeks during the second and third years; and every 24 weeks thereafter until PD. In addition, response assessments can be performed as clinically indicated to confirm response or progression.

- CT/PET/MRI/endoscopy
- Overall response assessment
- B-symptoms
- Laboratory Tests
 - Hematology
 - o MRD BMA (at CR only)
 - o Biomarker BMA (at CR only)
 - o MRD peripheral blood
 - o Biomarker peripheral blood
 - Bone marrow biopsy (at CR only, if baseline is positive for lymphoma or missing)
- Determination of Medical Resource Utilization (MRU)

8.2.3 End-of-Treatment Visit

- AEs
- Concomitant medications (including chemotherapy, radiation, over-the-counter drugs, vitamins, and herbs)
- ECG
- Determination of Medical Resource Utilization (MRU)
- Laboratory Tests
 - Hematology
 - o Blood chemistry
 - o Urinalysis
 - o Serum or urine pregnancy test for women of childbearing potential only
 - o MRD peripheral blood
 - o Biomarker blood
- Physical Exam
- Vital signs

8.3 Follow-up Phase

Once a subject has completed the End-of-Treatment Visit, they will enter the Follow-up Phase.

8.3.1 Response Follow-up

Subjects who discontinue treatment for reasons other than PD will participate in the response follow-up. From the time of first dose (Safety Run-in Period and TN open-label arm) or randomization (for Randomization Phase), these subjects will be followed every 12 weeks for the first year; every 16 weeks during the second and third years; and every 24 weeks thereafter until PD. Once subjects progress (for subjects who have not withdrawn consent), they will start the Long-term Follow-up.

8.3.2 Long-term Follow-up

Subjects in Long-term Follow-up will be contacted approximately every 12 weeks (±14 days) by clinic visit or telephone to assess survival and the use of alternative anticancer therapy. Subjects will be contacted until death, subject withdrawal, or study termination by the Sponsor, whichever occurs first.

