2.2.3 Exploratory Objectives

- To determine the prognostic significance of MRD negative remission by comparing the correlation to the efficacy outcomes in the two treatment arms.
- To evaluate whether the combination of ibrutinib and venetoclax will decrease MRD positive relapse in subjects who achieve MRD negative remission compared to ibrutinib and placebo.
- To evaluate the correlation of MRD negative remission in blood vs. bone marrow.
- To evaluate the correlation of MRD negative remission determined by flow cytometry and clonoSEQ.
- To evaluate PFS2: time from randomization to death or next disease progression (defined as the earliest of disease progression after the first subsequent anti-cancer therapy or start of the second subsequent therapy).
- To identify alterations in genes or proteins associated with sensitivity or resistance to the ibrutinib and venetoclax combination.
- To evaluate patient-reported outcomes as measured by European Organisation for Research and Treatment of Cancer Quality of Life Questionnaire EuroQoL Five-Dimension (EQ-5D-5L)
- To evaluate medical resource utilization (MRU) (eg, requirements of hospitalizations, emergency department visits, transfusions, and use of hematopoietic growth factors)

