- ^u Blood biomarker samples will be drawn at baseline, at documented complete response and onwards every 12 weeks (±7 days) for the remainder of the 1st year; every 16 weeks during the 2nd and 3rd years; and every 24 weeks thereafter until PD.
- V PK samples will be drawn at protocol-specified timepoints: pre-dose (30min), 1hr (±15min), 2hrs (±15min), 4hrs (±30min), 6hrs (±30min), and 8hrs (±1hr) post dose.
- W After progression, survival status, other malignancies and subsequent anticancer therapy will be collected approximately every 12 weeks (based on Week 1 Day 1 for a subject) until death, withdrawal by subject, loss to follow-up, or study terminated by Sponsor, whichever comes first.
- A unilateral bone marrow biopsy will be done at Screening or up to 28 days before the 1st administration of study drug for standard pathology. A 2nd bone marrow biopsy will be performed in subjects with positive bone marrow involvement at baseline by standard pathology who achieve a CR.

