Time to next treatment (TTNT)	Time from the date of randomization to the date of the initiation of subsequent anti-cancer treatment. Post-treatment stem cell transplantation, CAR T-cell therapy, or other cellular therapies are not considered subsequent anti-cancer treatments for subjects responding to the treatment (CR or PR). Subjects without the use of subsequent anti-cancer treatment will be censored at the last follow-up date for subsequent anti-cancer therapy.	Method is the same as for the PFS analysis	
Time to worsening in FACT- Lym subscale ^{5,6}	Time from the date of randomization to the start date of worsening (defined by a ≥5 points reduction from baseline) in the Lym Subscale or death due to any cause, whichever occurs first.	Method is the same as for the PFS analysis	
	Subjects who have not met the definition of worsening will be censored at the last non-missing post-baseline PRO assessment. Subjects without baseline or post-baseline assessment will be censored at the date of randomization.		

Page 27 of 35

Efficacy Endpoint	Definition	Analysis Method			
	Exploratory Endpoints				
Progression- free Survival Based on Investigator Assessment after Initiation of Subsequent Anti-cancer Therapy (PFS2)	Time from the date of randomization to the date of the earliest of the following three types of events: • PD per investigator response assessment after administration of the first subsequent anticancer therapy • Death at any time on study • Initiation of the second subsequent anticancer therapy Subjects who did not experience a PFS2 event will be censored at the last adequate response assessment or the last follow-up for subsequent anti-cancer therapy (if they no longer have response assessments).	No inferential test will be conducted. For each treatment arm, the KM estimate of the median PFS2 (mPFS2) and the KM estimates at selected landmark points will be calculated using the same methods as for the primary PFS analysis.			

CMH: Cochran-Mantel-Haenszel; CI: confidence interval; CR: complete response; HR: estimate hazard ratio; ORR: overall response rate; OS: overall survival; PD: progressive disease; PFS: progression-free survival; PR: partial response.

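### PFS2 counts progression after the next therapy, but for subjects who have already progressed the protocol neither schedules nor names collection of that progression

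*Protocol*

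**What the plan says.** **Objective.** Protocol 2.2.3 lists among the exploratory objectives: "To evaluate PFS2: time from randomization to death or next disease progression", with next progression meaning "the earliest of disease progression after the first subsequent anti-cancer therapy or start of the second subsequent therapy".

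**Analysis definition.** SAP 4.2 (Table 2) names three PFS2 events: "PD per investigator response assessment after administration of the first subsequent anticancer therapy"; "Death at any time on study"; and the start of a second subsequent therapy. Subjects without an event are censored at the last adequate response assessment or, if such assessments have ended, at the last follow-up for subsequent therapy. The analysis is Kaplan-Meier by arm (median and landmark estimates) with no test.

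**Data collected.** Protocol 7.2.1 runs investigator response assessment "until disease progression or withdrawal of consent from the study". Section 8.2.2 and Appendix A (footnote b) also end response visits at PD. Section 8.3.1 keeps subjects who stop treatment without PD in response follow-up, and moves subjects to long-term follow-up once they progress. Section 8.3.2 describes that follow-up as a contact about every 12 weeks, by visit or telephone, "to assess survival and the use of alternative anticancer therapy". The Appendix A footnote to the long-term follow-up column reads: "After progression, survival status, other malignancies and subsequent anticancer therapy will be collected approximately every 12 weeks". In the Appendix A grid, overall response assessment is marked for response visits and response follow-up but not for long-term follow-up.

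**The concern.** The first PFS2 event needs a progression date on the next line of therapy. On the usual path (first progression, next therapy, second progression), the subject has left response assessment before that date occurs, and the remaining contacts do not ask for it. The report would then carry a PFS2 median and landmark rates by arm under a definition that the data meet only in part.

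Two things are at stake. The estimates would be too long for most progressors. Capture would also depend on why treatment ended: a subject who stopped for toxicity and began a new therapy is still assessed, while a subject who progressed is not.

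**Working it through.** The documents give no PFS2 median, event count or power, so there is no figure to reproduce. The check sets the definition against the data and then works through the consequence.

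**1. Event types against collection, for a subject who has had a first PD**

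| PFS2 event (SAP 4.2) | Collected after first PD? | Where |
|---|---|---|
| PD after first subsequent therapy | Not scheduled, not named | Protocol 7.2.1, 8.2.2, 8.3.1, 8.3.2; Appendix A |
| Start of second subsequent therapy | Yes | Protocol 7.2.2, 8.3.2; Appendix A |
| Death | Yes | Protocol 7.2.2, 8.3.2; Appendix A |

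For a subject who starts a new therapy without prior PD, response follow-up under 8.3.1 runs until PD, so all three events can be recorded.

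**2. Direction**

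Let P be the time of PD after the first subsequent therapy, S the start of the second subsequent therapy, and D death.

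- As defined: T = min(P, S, D).
- As collected after first PD: T* = min(S, D).

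Removing a term from a minimum cannot make it smaller, so T* ≥ T for every affected subject. If P has occurred but neither S nor D has by the last therapy follow-up, the subject is censored event-free although the defined event has happened.

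**3. Size, as an illustration only**

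The size depends on the lag from P to min(S, D), which the documents do not give. In the simulations below, times are exponential unless a fixed lag is stated, and no second PD is recorded for progressors.

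*Set A.* The 14-month median first PFS is from protocol 10.3. Everything else is assumed: every first PFS event is a PD followed by next therapy; median time from first PD to second PD 4 or 8 months; 40% to 90% of subjects eligible for a further line, at a median lag of 0.5 to 2 months unless death comes first; median survival after second PD 4 to 8 months. Three results with the 4-month value:

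| Further line | Lag (months) | Survival after second PD (months) | Median PFS2 as defined | As collected | Excess |
|---|---|---|---|---|---|
| 90% | 0.5 | 4 | 20.3 | 21.5 | 1.2 |
| 70% | 2 | 8 | 20.3 | 25.5 | 5.2 |
| 40% | 2 | 8 | 20.3 | 28.3 | 8.0 |

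The first and last rows are the extremes of the grid. The 8-month value gives nearly the same excesses.

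*Set B.* Both design medians (14 and 23 months, protocol 10.3) are used. Assumed: 85% of first PFS events are PD; 1 month from PD to next therapy; median 5 months on next therapy; 30% to 70% start a further line 1 month after second PD; the rest die at a median of 3 to 6 months.

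| First PFS median | PFS2 as defined | As collected | Excess |
|---|---|---|---|
| 14 months | 21.6 | 23.5 to 27.5 | 1.9 to 5.9 |
| 23 months | 30.6 | 32.5 to 36.7 | 1.9 to 6.1 |

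The 5-month value lies within the 4 to 6.5 months of median PFS that protocol 1.1.2 cites for other agents. Those figures are not presented there as outcomes after ibrutinib.

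**4. Between-arm difference in set B**

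- As defined: 30.6 − 21.6 = 9.0 months.
- As collected, low end: 32.5 − 23.5 = 9.0 months.
- As collected, high end: 36.7 − 27.5 = 9.2 months.

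With the same post-progression assumptions in both arms, the gap in medians hardly moves.

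**The case against.** Several counter-arguments have force.

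- **Two of the three events are collected.** Start of a second subsequent therapy partly stands in for second progression, and a subject censored after an unrecorded second PD may still have an event later. This stands and limits the size. It does not remove the delay, since both proxies are already in the simulations.
- **The SAP anticipates the loss of response assessments.** Its censoring rule provides for subjects who no longer have them. That is true, so the change of endpoint is not hidden. The rule sets a censoring date; it does not recover the missing event.
- **The eCRF is not in the documents.** Protocol 7.2.2 says that subsequent lines are recorded without listing fields, so a progression date may be among them. A reader might infer that second progression is never captured; the documents support only that it is neither scheduled nor named after first PD.
- **No bias between the arms.** A reader might infer that the PFS2 comparison is distorted. Both arms share the same follow-up and the illustrated gap in medians is essentially unchanged. Uneven capture by reason for stopping treatment could differ by arm, but the documents give neither size nor direction.
- **Low stakes.** PFS2 is exploratory, untested, outside the hierarchy in SAP 1.6.1, and absent from the exploratory endpoints in protocol 10.2.4. This stands and sets the severity.

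**Conclusion.** The mismatch is real and minor. Followed as written, the protocol gives progressors a PFS2 that is in effect time to second subsequent therapy or death, and this can only equal or exceed PFS2 as the SAP defines it. The direction follows from the definition, provided that the progression date is not being collected through a form outside these documents.

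The size is not computable from the documents. About 1 to 8 months in the median is the range across assumed scenarios, and neither end should be read as an estimate for this trial. No primary, key secondary or safety conclusion is affected.

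**What to change.** 1. In protocol 8.3.2, the Appendix A long-term follow-up column and its footnote, add the date of investigator-determined progression on the first subsequent therapy, asked at the existing 12-weekly contact.
2. For subjects already in long-term follow-up, collect the date retrospectively from site records at the survival sweep (protocol 7.2.2).
3. Align the SAP PFS2 event wording so that this investigator-reported date counts. The present wording requires a response assessment, which a telephone contact does not clearly supply.
4. If the date is not collected, label and report the endpoint as time to second subsequent therapy or death, and use any PD recorded in response follow-up only in a sensitivity analysis.

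If the eCRF already holds this date, steps 1 and 3 only write down existing practice.

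**Cost.** One eCRF field, some retrospective site work and a short SAP edit, with no added scans or visits. The downside is that progression dates on the next therapy will not rest on protocol-scheduled imaging, which should be stated when PFS2 is reported.
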